5 PARTICIPANT SELECTION

During the course of the trial, approximately 350 sites will enroll approximately 5,840 subjects with TIA or minor ischemic stroke. Before enrolling subjects into the study, all collaborating sites will obtain approval from local IRBs or ethics committees, which will have access to all study documentation and educational materials.

5.1 Study Population

The study will include both TIA and minor ischemic stroke, with the latter accounting for no more than 50% of enrollment; if 2920 subjects with minor ischemic stroke are enrolled, only TIAs will be permitted in the trial subsequently. Most enrolled subjects will be elderly (mean age 72 years with 78% older than 60 years in the Northern California study), with about an equal number of males and females (53% were female in the Northern California study). Neurological impairment at the time of enrollment is expected to be minimal since the deficits prompting diagnosis will have largely resolved. Vascular risk factors, including diabetes, hypertension, and coronary artery disease, are expected to be common [16].

Pregnant women will be excluded from the study because the safety of clopidogrel is not established in this population, and this drug may increase risk of harm to the fetus. Women at risk for pregnancy (see Exclusion Criteria) will also be excluded. No other vulnerable population will be excluded from the study.

5.2 Inclusion and Exclusion Criteria

Inclusion Criteria

- Neurologic deficit (based on history or exam) attributed to focal brain ischemia and EITHER:
 - High risk TIA: Complete resolution of the deficit at the time of randomization AND ABCD² score ≥ 4
- OR**
- Minor ischemic stroke: residual deficit with NIHSS ≤ 3 at the time of randomization.
- Ability to randomize within 12 hours of time last known free of new ischemic symptoms.
- Head CT or MRI ruling out hemorrhage or other pathology, such as vascular malformation, tumor, or abscess, that could explain symptoms or contraindicate therapy.
- Ability to tolerate aspirin at a dose of 50-325 mg/day.

Exclusion Criteria

- Age <18 years.
- TIA symptoms limited to isolated numbness, isolated visual changes, or isolated dizziness/vertigo.
- In the judgment of the treating physician, a candidate for thrombolysis, endarterectomy or endovascular intervention, unless the subject declines both endarterectomy and endovascular intervention at the time of the evaluation for eligibility.
- Receipt of any intravenous or intra-arterial thrombolysis within 1 week prior to index event.
- Gastrointestinal bleed or major surgery within 3 months prior to index event.
- History of non-traumatic intracranial hemorrhage.
- Clear indication for anticoagulation (e.g., warfarin, heparin) anticipated during the study period (atrial fibrillation, mechanical heart valve, deep venous thrombosis, pulmonary embolism, antiphospholipid antibody syndrome, hypercoagulable state).
- Qualifying ischemic event induced by angiography or surgery.
- Severe non-cardiovascular comorbidity with life expectancy <3 months.
- Contraindication to clopidogrel or aspirin:
 - Known allergy

- Severe renal (serum creatinine >2 mg/dL or 176.8umol/L) or hepatic insufficiency (prior or concurrent diagnosis, with INR>1.5, or any resultant complication, such as variceal bleeding, encephalopathy, or icterus)
- Hemostatic disorder or systemic bleeding in the past 3 months
- Current thrombocytopenia (platelet count <100 x10⁹/l) or neutropenia/granulocytopenia (<1 x10⁹/l)
- History of drug-induced hematologic or hepatic abnormalities
- Anticipated requirement for long-term (>7 days) nonstudy antiplatelet drugs (eg, dipyridamole, clopidogrel, ticlopidine), or NSAIDs affecting platelet function (such as prior vascular stent or arthritis).
- Not willing or able to discontinue prohibited concomitant medications.
- Inability to swallow medications.
- At risk for pregnancy: premenopausal or postmenopausal woman within 12 months of last menses without a negative pregnancy test or not committing to adequate birth control (e.g., oral contraceptive, two methods of barrier birth control, or abstinence).
- Unavailability for follow-up.
- Signed and dated informed consent not obtained from patient.
- Other neurological conditions that would complicate assessment of outcomes during follow-up.
- Ongoing treatment in another study of an investigational therapy that may potentially interact with study drug, or treatment in such a study within the last 7 days.
- Previously enrolled in the POINT study.

6 TREATMENTS

6.1 Study Drugs

This randomized double-blind study is primarily designed to compare a clopidogrel/aspirin combination versus an aspirin alone regimen. The two types of study tablets (75 mg active clopidogrel and placebo) are indistinguishable, identical in size, shape, color, appearance, and taste.

Minor side effects are unusual with the medication [102], so it is not anticipated that either subjects or clinicians will be able to differentiate the placebo from the active drug. Standard laboratory tests cannot detect the effects of clopidogrel.

Investigators will not have access to the randomization (treatment) code, except in exceptional circumstances, such as occurrence of a serious adverse event for which knowledge of the study medication would be considered essential for treating the subject.

Sanofi supplied the blinded study drugs, clopidogrel 75mg and matching placebo, distributed by the UCSF Drug Product Service Laboratory (DPSL) for US sites and Pharmacy Services partners for OUS sites

in quantities sufficient to last through May 2016. From June 2016 forward, additional supplies of blinded study drug (clopidogrel and matched placebo) after that date will be provided by Sharp Clinical Services, Inc. in quantities sufficient to last through the end of enrollment.

Aspirin tablets will be open label with the dose in a range 50-325 mg daily determined by the treating physician. A dose of 150-200 mg daily x 5 days, followed by 75-100 mg daily will be strongly recommended.

The clopidogrel/aspirin group will receive the following treatment:

- Day 1*: 8 tablets of clopidogrel 75 mg (loading dose of 600 mg)
- From D2 to D90: one tablet of clopidogrel 75 mg and 50-325 mg of aspirin per day

The placebo/aspirin group will receive the following treatment:

- Day 1*: 8 tablets of placebo 75 mg (loading dose of 600 mg)
- From D2 to D90: one tablet of placebo 75 mg and 50-325 mg of aspirin per day

*Subjects will receive open label aspirin (50 mg – 325 mg), with dose at the discretion of the treating physician.

6.2 Assignment to a Treatment Group

The randomization will take place centrally via the WebDCU™. Subjects will be randomized 1:1 (clopidogrel: placebo), stratified by clinical center. The computer program developed at the NETT-SDMC makes the treatment assignment based on the current status of treatment group distribution within each clinical center as well as overall balance of treatment assignment.

7 STUDY DRUG HANDLING

7.1 Supply and Storage

The manufacturer Sanofi supplied the blinded study drugs (clopidogrel 75mg tablets, and placebo to match clopidogrel tablets) used in POINT and distributed by the UCSF Drug Product Services Laboratory (DPSL) to sites in the United States, and by Pharmacy Services partners to sites outside the US in quantities sufficient through May 2016. Additional supplies of study drug after that date will be provided by Sharp Clinical Services, Inc. in quantities sufficient to last through the end of enrollment.

There will be at least four drug shipments for the study: Sanofi will initially ship clopidogrel and placebo to the UCSF DPSL in April 2010 with a second shipment in 2012 and a third shipment will be sent in the second quarter of 2014. The fourth shipment will be handled by Sharp Clinical Services in May 2016. A fifth shipment may be necessary, and will depend on the expiration dates and the rate of enrollment into the study. After May 2016, supplies of study drug will be shipped directly from Sharp Clinical Services or the Pharmacy Services partner or depot to the research pharmacist/drug recipient at the POINT Clinical Site. Final verification of all study drugs will be completed by the research pharmacist or designee to ensure that the site maintains correct inventory.

Aspirin tablets will be open label with the dose in a range of 50-325 mg daily determined by the treating physician. A dose of 150-200 mg daily x5 days, followed by 75-100 mg daily will be strongly recommended.

All investigational drug supplies in the study will be stored in a secure, safe place, under the responsibility of the Investigator or other authorized individual, and under the conditions described on the labeling.

Study drug will be stored at a controlled room temperature of 25° C (77° F); excursions permitted to 15°- 30° C (59° - 86° F) Note: This temperature guideline should be followed; it differs from the USP guideline for controlled room temperature.

Storage temperature should be monitored and recorded daily, preferably by a continuous automated measuring and recording device. A daily manual temperature log must be maintained if automated temperature surveillance is not possible.

Systems must be in place for identifying and alerting staff when proper temperature storage conditions have been compromised (e.g., thermometer with alarm functions).

If storage conditions have been compromised (e.g., temperature exceeds allowable range) or if there is any suspicion that study product(s) have not been stored properly, the following actions must be taken:

- Quarantine study products suspected of improper storage
- Maintain products under correct storage conditions until further notice
- Contact the UCSF-CCC and, if necessary, Sanofi (through May 2016) and Sharp Clinical Services thereafter
- Document the occurrence, including amount of storage/temperature violation and amount of storage violation time
- Determine whether drug will need to be replaced and take steps to dispose of study drug and secure replacement drug

Procedures outlining roles and responsibilities should be in place at the local Pharmacy to ensure that storage issues have been addressed and rectified in an efficient manner. Sites will receive a template Local Site Pharmacy Standard Operating Procedures (SOP). This template SOP provides a customizable written format for documenting such procedures and responsibilities.

7.2 Packaging

Each subject will be assigned 97 tablets of study drug (eight (8) tablets for loading dose, and an 89-day supply for one tablet daily) according to the randomization assignment, to be used as directed.

The labels for shipments one to three, with computer-generated randomization codes that are to be used for the study drug bottles, will be produced centrally via the NETT SDMC, since the information on the labels is linked to the trial's randomization scheme. The labels have been designed in compliance with CA Code 4076 requirements for prescription container labeling and international guidelines. The labels for shipments four and five will be produced by Sharp Clinical Services and affixed to the bottles of study drug by Sharp.

7.3 Responsibilities

The Investigator, the Hospital Pharmacist, or other personnel allowed to store and dispense study drug will be responsible for ensuring that the study drug used in the clinical trial is securely maintained and in accordance with the applicable regulatory requirements.

All study drug shall be dispensed in accordance with the Investigator's prescription, and it is the Investigator's responsibility to ensure that an accurate record of study drug issued and returned is maintained. Any remaining drug will be destroyed by the site after a subject has completed participation.

Any quality issue noticed with the receipt or use of a study drug (deficient in condition, appearance, pertaining documentation, labeling, expiry date, etc.) should be promptly reported. Drug Accountability logs will be maintained within the WebDCU™ study database.

7.4 Concurrent Treatment

7.4.1 Prohibited Concomitant Treatments

Use of the following medications after randomization and during the study period represents a protocol violation. However, if there is a clinical need that justifies the added risk of these interventions in the setting of study drug use, they should be employed at the discretion of the treating physician.

- NSAIDs, Cox1 inhibitors. If absolutely necessary, NSAIDs may be given for as short a time as possible but not sooner than 8 days after randomization
- Anticoagulants (both oral and parenteral, see listing on CRF 18)
- Open-label thienopyridines (e.g., ticlopidine, clopidogrel)
- Dipyridamole
- Other antiplatelets
- Thrombolytics (e.g., tPA)
- Vascular intervention (surgery and / or angioplasty of any vessel).

If intervention is absolutely necessary within the three months after randomization, study drug will be stopped 5 days prior to the intervention. Study treatment will then be restarted unless the subject needs to take open label clopidogrel or aspirin. In this case, study drug will be restarted only when treatment with open label antiplatelet therapy other than aspirin has been stopped.

7.4.2 Permitted Concurrent Treatments

Any drugs other than those listed above are permitted at the discretion of the Investigator. Given uncertainty about an interaction between omeprazole and other proton-pump inhibitors (PPIs) and clopidogrel, those previously taking a PPI will be evaluated for the appropriateness of other agents, such as H2 blockers. New prescriptions for PPIs will be avoided whenever an H2 blocker or other agent is an acceptable option. Similarly, other drugs that theoretically may affect clopidogrel metabolism

will be avoided, with others substituted. This list includes: esomeprazole (Nexium), cimetidine (which is available by prescription Tagamet and OTC as Tagamet HB), fluconazole (Diflucan), ketoconazole (Nizoral), voriconazole (VFEND), etravirine (Intelence), felbamate (Felbatol), fluoxetine (Prozac, Serafem, Symbyax), and fluvoxamine (Luvox).

7.5 Treatment Discontinuation

The study drug should be continued whenever possible. If temporary interruption of study medication is required for surgery or other therapy, the subject's regimen will be resumed when it is considered safe by the subject's neurologist or primary care physician. Study medications will be restarted after carotid endarterectomy. If a clear indication for anticoagulation is revealed during the 90-day study period (atrial fibrillation, for example), study medications will be stopped and anticoagulation will be initiated.

If the study drug is stopped, it should be determined if the discontinuation can be made temporarily; permanent study drug discontinuation should be a last resort. Pregnancy will lead to definitive treatment discontinuation in all cases. In any case, all randomized subjects should remain in the study and followed per the protocol to 90 days from randomization, or to death, whichever comes first, even if the subject discontinues the POINT study drug regimen, unless the subject withdraws consent to participate in the trial.

7.5.1 Permanent Treatment Discontinuation

A subject should discontinue the study drug for any of the following reasons:

- Intercurrent condition that requires discontinuation of the study (e.g. lab abnormalities, surgical procedure, serious bleeding)
- Positive serum pregnancy test or desire to become pregnant
- Clear indication for anticoagulation (e.g., atrial fibrillation)
- Contraception cessation

Subjects will be followed according to the study procedures as specified in this protocol up to the scheduled date of study completion. All subjects who have discontinued the study drug will be followed per the protocol up to 150 days from randomization, or to death, whichever comes first, unless the subject withdraws consent to participate in the trial.

For subjects considered lost to follow-up, CRFs must be completed up to the last visit performed. For subjects who do not complete any assessments for the 90 Day visit, the Investigator should make every effort to contact the subject and to identify the reason why he/she failed to attend the visit and to determine his/her health status at 90 days by telephone contact with the subject or the subject's alternative contacts. Complete guidelines can be found in the CRF Data Collection Guidelines.

Subjects who have withdrawn consent from the study cannot be included again in the study. Their subject number and treatment must not be reused. The investigator will indicate treatment discontinuation and/or the subject's withdrawal in WebDCU™. Randomized subjects will not be replaced.

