8.5 SAEs/Clinical Outcomes

8.5.1 SAEs/Clinical Outcomes into the Study Database

All SAEs/Clinical Outcomes occurring until participation in study has ended are recorded on the online SAE/Clinical Outcome Reporting Form (CRF 19) through the WebDCU™. The Site PI or Study Coordinator is responsible for entering any and all SAEs into the database and updating the information (e.g., date of resolution, action taken), as needed, in a timely manner. Given the vast amount of data on AEs associated with clopidogrel, only SAEs/Clinical Outcomes will be recorded; data entry must take place within **5 days (within 24 hours for sites in the UK)** of discovery of the event.

The Hub PI for NETT sites and site PI for others are responsible for the monitoring and follow-up of all SAEs/Clinical Outcomes until resolution (or end of study for that subject) and appropriate documentation in the subject research record. In addition to performing protocol-specified follow-up,

the participating PI must review all previously reported ongoing SAEs/Clinical Outcomes to evaluate the current status.

Upon completion of the study by the subject, premature withdrawal from the study by the subject, or subject's death, all information regarding each SAEs/Clinical Outcome must be completed, if not done so earlier.

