9.4.2.1 Subjects Considered Lost To Follow-up

A subject is considered to be lost to follow-up (LTFU) when continued contact with the subject cannot be maintained and, despite an active follow-up effort, the site is unable to collect reliable information about the outcome event status of the subject up to 150 days following randomization (the 90 day enrollment period, and up to 60 days after the projected end of the subject's enrollment).

Information about outcome events that occurred during the subject's 90 day enrollment will be considered *reliable* when Form 14: Questionnaire for Verifying Stroke Free Status and/or Form 19: SAE/Clinical Outcome Reporting are completed based on contact with the subject, or the subject's caregiver or alternate contact. Events reported in this way will be adjudicated and included in the primary analysis.

A subject can be considered lost to follow-up when the clinical site can show documented attempts to reach the subject, and the period beyond the final scheduled study visit has reached 60 days (i.e., 150 days after randomization). For any subject who may be lost to follow-up, the POINT Clinical Site must discuss the subject with the appropriate NETT or CRC Study Manager and the UCSF Clinical Coordinating Center team before assigning that subject lost.

POINT Clinical Sites will need to demonstrate and document in WebDCU (Form 17 - End of Study: General Comments field) at least three (3) attempted telephone contacts by research personnel. A progress note, including the time and date of each attempt, should be added to the participant's study file for each contact. After attempts at phone contact are considered unsuccessful, or a subject has been reached but fails to appear for the 90 day visit, research personnel at sites must also generate and send at least one (1) letter using institutional letterhead and envelope. The letter should be sent

using Certified Mail™ with Return Receipt Service (or equivalent in other countries) for evidence of delivery to the participant's address, allowing a week for the subject to respond to the site. The receipt should be added to the participant's file, and a progress note, along with a copy of the letter(s), should also be placed in the subject's study file. When subjects cannot be contacted despite the site team implementing these approaches, investigators should attempt to determine the subject's vital status at 90 days (i.e., living or deceased) using locally-approved resources.

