### 4 STUDY DESIGN

The study is of a two-arm parallel design whereby eligible subjects are randomized in a 1:1 ratio to either the clopidogrel group or to the placebo group. Each subject is followed for 90 days from randomization.

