### 13.2 Summary of Adverse Events

All SAEs are summarized by "preferred term" and associated system-organ class according to the MedDRA adverse reaction dictionary and by treatment group in terms of frequency of the event, number of subjects having the event, timing relative to randomization, severity, and relatedness to the study drug.

For the following specific events, the proportions and their 95% confidence intervals by treatment group are provided:

- Death from any cause within 90 (± 14) days of randomization (expected rate 3%)
- Intracranial hemorrhage within 90 days (expected rate 0.5%)
- Major hemorrhage within 90 days (expected rate 2%)
- Minor hemorrhage within 90 days (expected rate 2%)

Expected rates of these events are based on historical data from the clopidogrel treated patients from pilot cohort studies ([name], et al., 2000; 2007), and these expected rates will be presented alongside the actual rates.

Other serious adverse events will be reported by treatment group. At the end of the study, the cumulative incidences of these events are compared between the two treatment groups using Fisher's exact test at the two-sided alpha level of 0.01.

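### Protocol 7.5.1 follows subjects who stop study drug to day 150 while the rest of the plan stops at day 90, and the SAE analyses with no stated window could therefore depend on discontinuation rates

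*Protocol*

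**What the plan says.** Two rules cover the same subjects. Protocol 7.5 says that "all randomized subjects should remain in the study and followed per the protocol to 90 days from randomization", and it applies this to subjects who stop study drug. Protocol 7.5.1 then says: "All subjects who have discontinued the study drug will be followed per the protocol up to 150 days from randomization". The sentence shortly before that one in 7.5.1 points back to the ordinary schedule: "Subjects will be followed according to the study procedures as specified in this protocol up to the scheduled date of study completion".

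The rest of the plan agrees with 90 days. SAP section 4 says "Each subject is followed for 90 days from randomization". Protocol 9.4.3 also follows each subject through day 90, 9.4.2.2 treats the 90 Day Visit as completion, and the schedule in 1.2 has no contact after day 90 ±14.

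Elsewhere, 150 days has a narrower meaning. Section 9.4.2.1 builds it as "the 90 day enrollment period, and up to 60 days after the projected end" for subjects who may be lost, and 8.5.3 says the search is for events within the subject's 90 days.

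On collection, Protocol 8.5.1 says: "All SAEs/Clinical Outcomes occurring until participation in study has ended are recorded". It names no day.

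On analysis, SAP 12.1.3 drops events after day 90 from the primary outcome. SAP 13.2 sets 90 days for intracranial, major and minor hemorrhage and 90 (±14) days for death. It gives no window for the summary of all SAEs or for other SAEs, where "the cumulative incidences of these events are compared between the two treatment groups" by Fisher's exact test at two-sided 0.01. The tertiary SAE analysis in SAP 12.5.2, overall and by MedDRA class, has no window either.

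**The concern.** A site cannot comply with both 7.5 and 7.5.1. If it follows 7.5.1, a subject who stops study drug may stay under observation 60 days longer than one who continues, and 8.5.1 can be read as requiring the SAEs of those 60 days to be recorded. Length of observation would then depend on an event after randomization.

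Fisher's test on the proportion of subjects with an SAE takes no account of observation time. If discontinuation differed between arms, the arm with more of it would have a longer average window and could show more SAEs with no drug effect. Serious bleeding is one of the reasons for stopping in 7.5.1, and Protocol 8.1 expects somewhat more major systemic hemorrhage on clopidogrel, so a higher discontinuation rate in that arm is plausible. What is at stake is the general SAE comparison in a trial whose main safety question is the harm of adding clopidogrel.

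**Working it through.** **Step 1: the follow-up rules side by side.**

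| Place | Who | Follow-up |
|---|---|---|
| Protocol 7.5 | all randomized, including discontinuers | day 90 |
| Protocol 7.5.1 | all discontinuers | day 150 |
| Protocol 9.4.3; SAP 4 | every subject | day 90 |
| Protocol 9.4.2.2 | end of participation | 90 Day Visit; day 150 only if lost to follow-up |
| Protocol 8.5.3, 9.4.2.1 | possibly lost subjects | tracing to 90 + 60 = 150 days, for events in days 0–90 |

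Only 7.5.1 extends follow-up itself. It names all discontinuers and deals with lost subjects in a separate paragraph, so its wording does not limit the 150 days to tracing.

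**Step 2: inputs for the size.** The plan gives no SAE rate overall, no discontinuation rate by arm and no calculation on this point, so there is no figure of its own to reproduce. From the documents: 5,840 subjects randomized 1:1 (SAP 5.3 and 4), so n = 2,920 per arm; windows of 90 and 150 days; test level 0.01 (SAP 13.2). Assumed: no true SAE effect, a constant hazard, a 90-day SAE risk s, and a share d of each arm that discontinues and is followed to day 150 with SAEs recorded.

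**Step 3: formulas.**
- Mean window in an arm = 90 + 60d days.
- 150-day risk r = 1 − (1 − s)^(150/90). For s = 10%, r = 1 − 0.90^1.667 = 16.1%.
- Observed proportion in an arm = d·r + (1 − d)·s.
- z = difference / √(2·p̄(1 − p̄)/2,920), where p̄ is the mean of the two proportions.
- Rejection rate = Φ(z − 2.576) + Φ(−z − 2.576), a normal approximation to Fisher's test.

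**Step 4: results.**

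| s | Discontinuation | Mean window (days) | Observed SAE proportion | z | Rejection at nominal 0.01 |
|---|---|---|---|---|---|
| 10% | 20% v 21% | 102.0 v 102.6 | 11.22% v 11.28% | 0.07 | 0.010 |
| 10% | 20% v 25% | 102.0 v 105.0 | 11.22% v 11.53% | 0.37 | 0.015 |
| 10% | 20% v 30% | 102.0 v 108.0 | 11.22% v 11.83% | 0.73 | 0.033 |
| 15% | 20% v 30% | 102.0 v 108.0 | 16.75% v 17.62% | 0.88 | 0.046 |

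The normal approximation runs slightly high. Simulating Fisher's test itself (4,000 runs) for s = 10% and 20% v 30% gave about 0.027.

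**Step 5: sensitivity to the constant hazard.** Protocol 2.6 reports that 73% of composite vascular events in its emergency-department cohort fell in the first month. Suppose SAEs followed that pattern (an assumption) and days 91–150 matched days 31–90. Then r = 10% + 0.27 × 10% = 12.7%. Discontinuation of 20% v 25% gives 10.54% v 10.68% and rejection of about 0.011; 20% v 30% gives 10.54% v 10.81% and about 0.014. In the other direction, suppose discontinuers had three times the hazard after day 90. Then r = 1 − 0.90 × 0.90^(3 × 60/90) = 27.1%, and 12% v 20% gives 12.1% v 13.4%, with simulated rejection of about 0.15. The documents support no such multiplier.

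**Step 6: with one common cut-off.** If SAEs count only up to day 90 in every subject, both windows are 90 days, the artificial difference is zero, and the test stays at or below 0.01.

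**The case against.** The strongest reply is that the chain may never start. Protocol 9.4.2.2 ends participation at the 90 Day Visit, so a discontinuer who attends it has left the study and 8.5.1 no longer asks for SAEs. No visit is scheduled after that window, and the sentence shortly before the disputed one in 7.5.1 runs follow-up to scheduled completion. The 150 days may simply be carried over from the lost-to-follow-up rule, though that is an inference. This stands as a reason to doubt that all sites would extend follow-up. It does not remove the contradiction, because 7.5.1 is current text and sites could read it differently.

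A reader might infer that the clopidogrel arm will be observed longer and will show excess SAEs, or that the safety comparison as a whole is compromised. The documents support neither.
- Differential observation needs three conditions together: sites apply 7.5.1, SAEs after day 90 are recorded despite 9.4.2.2, and discontinuation differs by arm.
- The primary safety outcome, major hemorrhage, is limited to 90 days, as are intracranial and minor hemorrhage; death is limited to 90 (±14) days. SAP 12.1.3 also says its ITT analysis, which drops events after day 90, is repeated for the primary and secondary safety outcomes.
- The only between-arm difference in a cause of stopping that the documents quantify is about 1 point of excess major systemic hemorrhage (Protocol 8.1). At a gap of that size the effect is negligible.
- A subject whose SAE caused the stop is already counted, so extra days add nothing for that subject in an any-SAE proportion, although they can in class-level analyses. The illustration ignores this.

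**Conclusion.** The contradiction over follow-up is certain, and SAP 13.2 and 12.5.2 leave the affected SAE analyses without a window. The bias is conditional. It could reach only the all-SAE summary, the Fisher comparison of other SAEs and the tertiary SAE analysis, and only if the three conditions above hold.

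Its size rests on assumed rates. At 10% SAE risk with a constant hazard, the rejection rate is about 0.010 for a discontinuation gap of about 1 point, and about 0.015 to 0.033 for gaps of 5 to 10 points. Front-loaded SAEs would lower these figures; a higher SAE risk, or a raised hazard among discontinuers, would increase them. The primary efficacy outcome, the hemorrhage outcomes and death are not exposed in this way. The point is one of consistency and of an unstated counting window, and it should be corrected because a rule in the protocol, if followed, makes SAE observation time depend on a post-randomization event.

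**What to change.** 1. **Protocol 7.5.1.** Reconcile the 150-day sentence with 7.5, 8.5.1, 9.4.2.1 and 9.4.2.2, so that day 150 serves only as the limit for contact attempts to establish a subject's status at day 90, whether or not study drug was stopped.
2. **SAP 13.2 and the SAE line of 12.5.2.** State that between-arm SAE summaries and tests count SAEs with onset on or before day 90 from randomization, in both arms and for every subject. List later SAEs separately, by arm, without a test.

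The cost is one protocol sentence and one or two SAP sentences. No new data are needed, since SAP 13.2 already summarises SAE timing relative to randomization. Later SAEs remain visible in the listing, so no safety information is lost.
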